RCT: Study staff will contact enrolled participants, complete baseline assessments, and randomize to the adapted STAT-ED or control condition (enhanced Treatment as Usual). The adapted STAT-ED will involve the following strategies: psychoeducation, motivational interviewing, problem solving logistical barriers, and assistance with making and following up with mental health appointments. This could involve identifying additional mental health resources and providers based on insurance type. One social worker has been hired and trained to implement the adapted STAT-ED and the control condition (enhanced Treatment as Usual) for study. Patient navigator will communicate with the family in person, by telephone, and/or by text messaging via family's preference. The control condition (enhanced Treatment as Usual) will receive telephone contacts to check in and remind families about mental health care initiation. Telephone contacts are consistent with current ED practice in which social work team members follow up by telephone with patients and their caregivers about referrals given at ED discharge. The proposed study is a small pilot to adapt a patient navigator intervention for suicidal Black youth and test the preliminary effectiveness of the intervention in preparation for a fully-powered RCT. We will perform initial analyses (chi-square and *t*-tests) to compare the intervention and control groups on proportion to initiate mental health treatment, mean number of days to treatment initiation, and mean number of treatment sessions at both 2 months and 6 months follow-up. A Cox proportional hazards model will examine group differences in mental health utilization, time to treatment initiation, suicidal ideation, and mental health motivation (Cox, 1972). Assessments may be conducted in-person, via telephone, or electronically/online. At the end of the study, we will also solicit and review feedback from the patient navigator who is research staff member about feasibility and acceptability. The patient navigator will also complete fidelity measure after first session of the adapted STAT-ED.

Participants may be recontacted to update information or to see if they are interested in participating in other research.

3.2 Allocation to Treatment Groups and Blinding.

In the RCT, subjects will be randomized to either the adapted STAT-ED or to enhanced treatment as usual. Randomization will be accomplished in advance using computer-

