4.2.2 Visit 2**RCT**

- Youth and caregiver report measures (MYTS, SIQ-Jr, ED STARS, AIM)
- Assess possible adverse events
- Medical Health Record Review

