4.2.3 Visit 6: End of Study

The end of the study visit for randomized trial is at 6 months after baseline assessment. Youth and caregiver report measures are administered (MYTS, SIQ-Jr, ED STARS, intervention acceptability survey). Adverse events will be assessed.

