5.1.2 Other Evaluations, Measures

Qualitative Interviews

- *Qualitative interview guide* will be developed. Questions concerning perceptions and preferences of mental health treatment and barriers and facilitators to accessing mental health services will be asked of participants.
- *Demographics survey* will gather information such as age, biological sex, gender, race/ethnicity, sexual orientation, and family income.

Field Testing

- *Demographics survey* will gather information such as age, biological sex, gender, race/ethnicity, sexual orientation, and family income.
- *Patient navigation notes*

RCT

- ED STARS mental health service use is a 8-item interview that measures mental health services children receive and actions taken by family to obtain services. This measure was used with over 6000 adolescents from the Pediatric Emergency Care Applied Research Network (PECARN) that spanned diverse geographic regions of the US (King et al., 2020). Caregivers will complete this interview unless youth is participating without a parent.
- *Motivation for Youth's Treatment Scale (MYTS)* is an 8-item measure of intrinsic treatment motivation that has both youth and parent reports (Breda et al., 2012). It has two subscales: recognition that the youth has a problem and readiness to participate in the youth's treatment. It has good internal consistency and validity with support for the factors. MYTS has a 5-point Likert scale with higher scores representing higher motivation. MYTS will be completed by youth and caregivers.
- *Suicide Ideation Questionnaire-Junior (SIQ-Jr)* is a youth report measure of frequency of suicidal thoughts over the last month (Reynolds, 1988). SIQ-Jr has high internal consistency, test-retest reliability, predictive validity for suicidal behavior, and is sensitive to change (Reynolds & Mazza, 1998).
- Acceptability of Intervention Measure (AIM), a 4-item, psychometrically-validated measure that indexes the extent to which stakeholders believe an intervention is acceptable. Both youth and a caregiver will rate the intervention helpfulness and satisfaction. Additionally, the patient navigator will complete the AIM after the trial is completed.

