5.2 Efficacy Evaluations

In the RCT, these are the measures that will be used to assess efficacy (mental health utilization)- ED STARS. The three primary efficacy outcomes are 1) whether the patient initiated mental health treatment (yes/no), 2) time to treatment initiation, and 3) number of

treatment sessions attended. Other outcomes are suicidal ideation and behavior measured by SIQ-Jr.

5.2.1 Diagnostic Tests, Scales, Measures, etc.

In the qualitative interviews, the research staff will conduct semi-structured interviews with questions concerning perceptions and preferences of mental health treatment and barriers and facilitators to accessing mental health services with youth and caregiver participants. In the field testing, participants will not complete any measures or scales. . In the RCT, ED STARS is an interview and will be administered by research staff to caregivers at 2 (Study visit 2) and 6 months (final visit) after baseline assessment. SIQ-Jr is a self-report measure that will be administered to youth at baseline and 2 and 6 months after baseline assessments.

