6.3.2 Efficacy Analysis

These are the measures that will be used to assess efficacy (mental health utilization), ED STARS. The three primary efficacy outcomes are 1) whether the patient initiated mental health treatment (yes/no), 2) time to treatment initiation, and 3) number of treatment sessions attended. Other outcomes are suicidal ideation and behavior which will be examined by changes in total score over time from baseline to Visit 2 and final Visit.

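### Section 3.1.2 assigns a Cox model to suicidal ideation (SIQ-Jr) and motivation (MYTS), which are repeated scores with no defined event, and no usable between-arm analysis is stated for either

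*Combined protocol and SAP*

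**What the plan says.** The analysis sentence is in the RCT paragraph of section 3.1.2: "A Cox proportional hazards model will examine group differences in mental health utilization, time to treatment initiation, suicidal ideation, and mental health motivation". The sentence before it names chi-square and t-tests, but only for the proportion initiating treatment, days to initiation and number of sessions.

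The two scores are described in section 5.1.2. The SIQ-Jr "is a youth report measure of frequency of suicidal thoughts over the last month". For motivation, "MYTS has a 5-point Likert scale with higher scores representing higher motivation. MYTS will be completed by youth and caregivers".

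The schedule is fixed. Section 4.2.1 and Table 1 place both instruments at baseline. Section 4.2.2 lists "Youth and caregiver report measures (MYTS, SIQ-Jr, ED STARS, AIM" at Visit 2, and section 4.2.3 covers the 6-month visit: "Youth and caregiver report measures are administered (MYTS, SIQ-Jr, ED STARS, intervention acceptability survey". Section 5.2.1 confirms that "SIQ-Jr is a self-report measure that will be administered to youth at baseline and 2 and 6 months after baseline assessments".

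The statistical section treats suicidal ideation differently. Section 6.3.2 says it will be "examined by changes in total score over time from baseline to Visit 2 and final Visit". MYTS does not appear in sections 5.2 or 6.1 to 6.3.

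**The concern.** A Cox model needs, for each participant, a time from a defined origin to a defined event, or to censoring. A score recorded at three scheduled visits supplies none of these. To apply the model to SIQ-Jr, someone would have to choose a threshold, decide whether the event is onset, worsening or remission, and decide how to treat youth already past the threshold at baseline. The documents make none of these choices, and any hazard ratio would depend on them.

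Suicidal ideation is the secondary efficacy outcome in section 2.1 and one of the main RCT outcomes in the abstract. With an unworkable method in 3.1.2 and an incomplete one in 6.3.2, the plan does not fix which treatment effect on ideation will be reported. Section 6.4 intends the pilot's effect sizes to feed the sample size of a later trial. A mean difference with its SD would serve that purpose. A hazard ratio built on a cut-point chosen after the data are seen would not.

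**Working it through.** The plan gives no figure to reproduce on this point. The check sets the passages side by side and then does some short arithmetic.

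**1. Outcomes in the Cox sentence against what is measured**

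| Outcome in 3.1.2 | How it is measured | Does Cox fit? | Other analysis stated |
|---|---|---|---|
| Time to treatment initiation | ED STARS interview | Yes | t-test on mean days (3.1.2) |
| Mental health utilization | ED STARS; covers initiation and a session count | For initiation only, not the count | chi-square for initiation, t-test for sessions (3.1.2) |
| Suicidal ideation | SIQ-Jr score, last-month recall | No event defined | Change in total score, no model and no between-arm contrast (6.3.2) |
| Mental health motivation | MYTS score, youth and caregiver | No event defined | None |

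The scores cannot be read as covariates, because the sentence speaks of differences between groups in them. Section 6.3.2 does not name SIQ-Jr; the link comes from section 5.2, which names it as the measure of suicidal ideation and behavior.

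**2. Comparisons without a usable stated method**

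- SIQ-Jr: 1 reporter × 2 post-baseline visits = 2
- MYTS: 2 reporters × 2 post-baseline visits = 4
- Total: 2 + 4 = 6

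This is a minimum. Section 5.1.2 gives MYTS two subscales, and the plan does not say whether a total or the subscales are analysed.

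**3. Could event dates be recovered from SIQ-Jr?**

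With a one-month look-back, the 2-month visit covers months 1 to 2 and the 6-month visit covers months 5 to 6. That is 1 + 1 = 2 of the 6 follow-up months. The other 6 − 2 = 4 are unobserved, and within the covered months the instrument records frequency, not dates.

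**4. Precision of the suggested replacement (illustrative)**

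The assumptions are these:
- N = 42 youth. Section 3.3.2 expects 85 evaluable subjects counted as individuals; if half are youth, 85 / 2 = 42.5, taken as 42.
- 21 per arm. No allocation ratio is stated, so 1:1 is assumed.
- Equal SDs σ at both visits and normal scores.
- Baseline-to-follow-up correlation r, which the documents do not give.

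With n per arm:
- Var(change-score difference) = (2/n) σ² × 2(1 − r)
- Var(ANCOVA difference) = (2/n) σ² × (1 − r²) × [1 + 1/(N − 4)]
- Ratio of ANCOVA to change score = [(1 + r)/2] × (1 + 1/38) = [(1 + r)/2] × 1.026

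| r | (1 + r)/2 | Variance ratio |
|---|---|---|
| 0.3 | 0.65 | 0.667 |
| 0.5 | 0.75 | 0.770 |
| 0.7 | 0.85 | 0.872 |

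A simulation of 40,000 trials gave 0.675, 0.766 and 0.874. The two methods break even where (1 + r)/2 = 1/1.026, that is at r of about 0.95. Baseline adjustment is therefore the more precise choice over this range even at pilot size. This supports the suggested fix; the defect does not depend on it.

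**The case against.** The strongest reply is that section 3.1.2 is narrative and section 6.3.2 is the efficacy analysis. The latter gives change in SIQ-Jr total score, and the talk of group differences in 3.1.2 and 6.4 points to comparing that change between arms. On this reading only one stray term and one missing sentence are at issue. Part of this stands: a comparison of change scores is probably intended, and stating it would be enough. But 6.3.2 names neither the contrast nor the model, 3.1.2 names a different and unworkable model for the same outcome, and nothing in 6.3.2 helps MYTS.

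The pilot setting also lowers the stakes. Section 6.4 disclaims any intention to show statistical significance and puts feasibility first. Sections 5.2 and 6.3.2 class ideation as an other outcome, and MYTS is not a listed endpoint. That limits the severity. It does not make a Cox model definable for a score, and the same section relies on the effect sizes obtained.

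Three narrower points are fair:
- Discrete-time or interval-censored methods do not need exact event dates, so the recall window is secondary to the missing event definition.
- Time to treatment initiation also lacks a stated origin and censoring rule. An origin at baseline can be inferred, and the event is clear, so Cox remains suitable there; the details should still be written down.
- Utilization can be read as the umbrella term for ED STARS, since section 6.3.2 says "These are the measures that will be used to assess efficacy (mental health utilization), ED STARS". The session count has its own t-test, so no utilization outcome is left without a method.

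**Conclusion.** The concern holds and should be fixed. For two of the four outcomes in the Cox sentence the stated analysis cannot be run, because no event is defined. For suicidal ideation it also conflicts with section 6.3.2, which is itself incomplete. For motivation no other analysis exists. At least six post-baseline between-arm comparisons are affected, counting one MYTS score per reporter.

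The reach is limited to secondary and other outcomes. The three primary outcomes have suitable methods named (chi-square, Cox, t-test), and Cox for time to treatment initiation is not disputed. This conclusion rests on the text alone. Only the variance ratios depend on assumptions (42 youth, 21 per arm, equal SDs, normal scores, and correlations of 0.3 to 0.7).

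**What to change.** - In section 3.1.2, limit the Cox model to time to treatment initiation. State its time origin and censoring rule in the same edit. Leave the session count to the t-test already named for it.
- In sections 3.1.2 and 6.3.2, state one between-arm analysis of SIQ-Jr and of the youth and caregiver MYTS scores at 2 and 6 months. ANCOVA or a linear mixed model with the baseline score as covariate is one suitable choice. An explicit between-arm comparison of change scores would also repair the text, with less precision under the assumptions shown.
- Say whether MYTS is analysed as a total or by subscale.
- Report the adjusted mean difference, its 95% confidence interval and the SD at each visit.

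The cost is a few sentences, made before analysis. No new data are needed, because the baseline, 2-month and 6-month scores are already in the visit schedule.

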4.2 Study Treatment Phase

This will include the qualitative interviews, field testing, and RCT. Medical Health Record Review will not access protected mental health records.

4.2.1 Visit 1

Qualitative interviews

- Informed Consent/Accent
- Medical Record Review
- Review of Inclusion/Exclusion Criteria
- Recorded semi-structured interview
- Demographics questionnaire

Field Testing

- Review of Inclusion/Exclusion Criteria
- Informed consent/assent
- Demographics questionnaire
- Field testing procedures

RCT

- Medical records review
- Review of inclusion/exclusion criteria
- Youth and caregiver report measures (MYTS, SIQ-Jr, PANAS, demographics questionnaire)
- Randomization
- Intervention

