6 STATISTICAL CONSIDERATIONS

6.1 Primary Endpoint

Primary endpoint for qualitative phase (interviews and field testing): themes of caregiver and youth mental health attitudes and engagement and an adapted STAT-ED manual
Primary endpoint for randomized trial: mental health treatment initiation. The three primary efficacy outcomes are: a) whether the patient initiated mental health treatment (yes/no), b) time to treatment initiation, and c) number of treatment sessions attended.

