6.3 Statistical Methods

6.3.1 Baseline Data

For qualitative interviews, caregiver and youth interviews will be analyzed using EHOST open source analysis software. Initial codes will be developed inductively through investigative team consensus. Themes pertaining to child, family, clinician and systemic barriers and facilitators, motivation for treatment, receipt and perceptions of mental health services will be identified. After initial exploration, a comprehensive coding scheme will be developed and applied to all data to produce a fine-grained descriptive analysis.

For the RCT, descriptive statistics for demographic and behavioral characteristics measured at baseline will be examined across the two treatment groups to assess the success of the randomization.

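### Baseline treatment motivation (MYTS) is measured before randomisation, but no baseline covariate is pre-specified for the session-count and time-to-initiation analyses

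*Combined protocol and SAP*

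**What the plan says.** **Timing.** Section 3.1.2 (RCT) has staff "complete baseline assessments, and randomize to the adapted STAT-ED or control condition", in that order. Section 4.2.1 lists for RCT Visit 1 "Youth and caregiver report measures (MYTS, SIQ-Jr, PANAS, demographics questionnaire"), ahead of randomisation.

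**The measure.** Section 5.1.2 describes MYTS as an "8-item measure of intrinsic treatment motivation that has both youth and parent reports". Its subscales cover "recognition that the youth has a problem and readiness to participate in the youth's treatment". Youth and caregivers both complete it.

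**The outcomes.** Section 6.1 lists three primary efficacy outcomes: whether treatment was initiated, "b) time to treatment initiation, and c) number of treatment sessions attended".

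**The analyses.** Section 3.1.2 plans chi-square and t-tests on the proportion initiating, "mean number of days to treatment initiation, and mean number of treatment sessions at both 2 months and 6 months follow-up". It then adds: "A Cox proportional hazards model will examine group differences in mental health utilization, time to treatment initiation, suicidal ideation, and mental health motivation". Motivation appears there as something to be compared between arms, not as a covariate. Section 6.3.2 lists the outcomes without a model or covariate.

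**Use of baseline data.** Section 6.3.1 says that baseline demographic and behavioural characteristics "will be examined across the two treatment groups to assess the success of the randomization". It does not mention MYTS by name and gives no adjustment rule. Sections 3.2 and 8.1.1 describe computer-generated random numbers and sealed envelopes, with no stratification.

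**The concern.** The primary outcomes ask whether, when and how much a youth takes up treatment. A baseline score for motivation and readiness for treatment is a plausible predictor of all three, and it is in hand before allocation. The plan does not say that it will be used.

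Two things are at stake. First, if motivation is prognostic, an unadjusted session-count comparison is less precise than it could be, and an unadjusted Cox model has less power. Section 6.4 says the pilot's effect sizes will inform the sample size of the next trial, so the quality of the estimates matters even though the pilot is not meant to show significance. Second, the Cox sentence leaves adjustment open, and a balance table will be produced. Without a rule, the covariates could be chosen after that table has been seen.

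**Working it through.** **Inputs.** Section 3.3.2 gives 50 dyads and 85 evaluable of 100 participants. That is 50 youth, or 50 × 0.85 = 42.5, about 42 evaluable. With 1:1 allocation (not stated) there are 25 or 21 per arm. Two-sided alpha of 0.05 is also assumed. The correlation r between baseline MYTS and outcome is not in the documents, so a range is shown.

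**The plan's own power figure.** Section 6.4 pairs 80% power with f = .72. In a two-group comparison f = .72 is d = 1.44, which gives power 0.995 with 42 youth. The f that gives 80% with 42 youth is 0.443 (d = 0.886). The stated figure therefore does not reproduce in this form. That is a separate matter; 80% serves below only as a reference level.

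**Session count, treated as continuous.** Adjustment multiplies the variance by 1 − r² and the standard error by √(1 − r²). The difference detectable with 80% power is (1.96 + 0.84) × √(2/n) × √(1 − r²), in SD units. Power starts from d = 0.886 at 21 per arm, using d/√(1 − r²) and one fewer degree of freedom.

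| r | Variance cut | SE factor | Detectable difference, 25 per arm | 21 per arm | Power (reference 80%) |
|---|---|---|---|---|---|
| 0 | 0% | 1.00 | 0.792 | 0.865 | 80% |
| 0.2 | 4% | 0.98 | 0.776 | 0.847 | 81.5% |
| 0.3 | 9% | 0.954 | 0.756 | 0.825 | 83.5% |
| 0.5 | 25% | 0.866 | 0.686 | 0.749 | 89.8% |

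Estimating the covariate slope raises the standard error by about √(1 + 1/38) = 1.013 at 21 per arm, which the table leaves out. Including it lowers each power figure by about one point, so r near 0 brings a loss of about that size.

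**Chance imbalance.** The between-arm difference in mean baseline MYTS has SD √(2/n): 0.283 at 25 per arm and 0.309 at 21, in MYTS SD units. It exceeds 0.25 SD in 38% or 42% of randomisations, and 0.5 SD in 8% or 10%. It reaches the outcome multiplied by r: a 0.5 SD imbalance at r = 0.3 moves the session difference by 0.5 × 0.3 = 0.15 SD.

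**Cox model, simulated.** Assumed: 42 youth, 40% of controls initiating by 6 months, exponential times, conditional hazard ratio 3, standard normal covariate.

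| Log HR per SD of MYTS | Power unadjusted | Power adjusted | Median unadjusted HR |
|---|---|---|---|
| 0 | 76% | 76% | – |
| 0.3 | 72% | 74% | 2.90 |
| 0.5 | 67% | 73 to 74% | 2.76 |
| 0.7 | 58% | 71% | 2.55 |

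Allowing for simulation error, the gains are about 2, 6 to 8, and 13 points. The spread of the estimate does not fall: at 0.5 per SD the SD of the log hazard ratio rose from 0.439 to 0.466 with adjustment.

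A second scenario (50 youth, about 50% of controls initiating by 180 days, HR 2) shows the same pattern. Power rose from 44% to 47% at 0.3 per SD and from 35% to 45% at 0.6, while the standard error went from 0.373 to 0.380 and from 0.372 to 0.383.

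Under no treatment effect, rejection rates in this second set-up, run with 42 and 50 youth, were about 4 to 5% with or without adjustment.

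**The case against.** **A reader might infer that the plan commits to an unadjusted Cox model.** It does not. Only the chi-square and t-tests are unadjusted by construction; the Cox sentence is silent on covariates.

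**A reader might infer that the unadjusted hazard ratio is biased towards 1.** The documents give no ground for that. With 2,000 youth in the same simulation, the unadjusted ratio still settles at 2.73 (0.5 per SD) or 2.55 (0.7 per SD). That is the marginal hazard ratio, which differs from the conditional one because hazard ratios are non-collapsible. It is a valid estimate, and it is the relevant planning input if the next trial is analysed unadjusted.

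**A reader might infer that chance imbalance in motivation undermines the result.** Imbalance enters only in proportion to an undocumented correlation, and the unadjusted standard error already allows for it. It moves the estimate in one sample but does not invalidate the test.

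**MYTS is not shown to be the only or best covariate.** The RCT exclusion in 3.4.2.3 covers current treatment only. Past treatment is allowed, and section 5.1.1 lists a chart review for mental health treatment, without protected mental health records. SIQ-Jr, age and insurance type are also collected. This stands: MYTS is a sensible choice on content, not a proven one.

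**The caregiver report could be missing selectively.** Section 5.1.2 allows for youth taking part without a parent. This stands and decides the informant in the fix.

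**The trial is a pilot not intended to detect significant differences.** That lowers the weight of power gains, but not of precision in estimates that will be carried forward. The initiation yes/no comparison stays an unadjusted chi-square here; the point does not extend to it.

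**Conclusion.** The point holds as a missing pre-specification, not as an error in the planned tests. MYTS is available before randomisation, the session-count test ignores it, and the Cox sentence and section 6.3.2 do not say whether it will be used.

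For the session count the loss is one of precision: small up to r of about 0.3 and material at 0.5. For time to initiation the loss is one of power against a conditional hazard ratio, with no reduction in standard error. Both sizes rest on assumed prognostic strength, 1:1 allocation, two-sided 0.05 and, for Cox, the assumed initiation rate and hazard ratio. If MYTS has no prognostic value, nothing is gained and about one point of power is lost. The change is worthwhile because it is cheap and closes off a choice that could otherwise be made after the data are seen.

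**What to change.** In sections 3.1.2 and 6.3.2, pre-specify baseline MYTS total, youth report, as the single covariate in two models: the session-count analysis (ANCOVA or a count regression) and the Cox model for time to initiation. The youth report is preferred because it does not depend on a caregiver taking part.

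State also that:
- the unadjusted result will be reported alongside each adjusted one;
- the adjusted hazard ratio is conditional on baseline motivation, and the unadjusted one is marginal;
- covariates will not be chosen from the balance table in 6.3.1;
- follow-up MYTS will not be used as a covariate, because it is measured after randomisation and the motivational interviewing may change it;
- how a missing baseline score will be handled.

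The cost is a few sentences and one degree of freedom, with no new data. The remaining downside is interpretive: whoever plans the next trial will have a conditional and a marginal hazard ratio and must use the one that matches that trial's analysis.
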